2 INTRODUCTION

2.1 Clinical Study Summary

Number of Sites	1 – 2
Number of Subjects	A minimum of 10 male and 10 female subjects 12 years of age and younger, with an overall minimum of 28, and maximum of 33 subjects
Objective	
The primary objective of this study is to gather clinical data as follows:
 
 To confirm that the T-DOC® 5 French vesical and abdominal catheters are safe and effective for measuring urodynamic pressure in pediatric subjects 12 years of age and younger. 
The secondary objective of this study is to gather user feedback regarding device performance as follows:
 
 To evaluate the following subjective measures using defined ordinal scales: ease of use, presence of artefacts, stability of the tracing, perceived time savings, ease of voiding around the catheter, presence of use errors, and overall satisfaction.
Inclusion criteria	
 Male and Female (Children, 12 years of age and younger) Subjects who are scheduled and normally indicated for urodynamic testing, for any medically necessary reason as per physician discretion.
Exclusion criteria	
 Subjects who suffer from bladder infections (not including subjects with asymptomatic bacteriuria) Subjects with urethral strictures Subjects who require the use of a suprapubic catheter
Anticipated Study duration	
The proposed recruitment phase following site initiation is 12 weeks (first subject in to last subject out).
 
Subjects will come to the clinic for one visit, their urodynamic procedure, where data pertaining to the safety, efficacy and usability aspects of catheter will be collected.
 
Test duration may be slightly longer than a standard test while assessment of the study materials is being made, and so discomfort and inconvenience associated with an extended test duration may occur.

Follow-up	Subject follow-up will occur 5-7 days following the test to collect information about any adverse events post-test.

Study end point

Once the minimum subject recruitment goal is met, the sponsor will be informed. Sites will have an option to continue recruitment until the maximum is reached, given recruitment does not exceed the allocated timeline. There will be a site monitoring visit where the site will be closed out.

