12.4 Sample Size Determination & Power

Sample size calculations were and will be performed in accordance with Binomial Distribution theory (except for the second exploratory objective), utilizing the following formula:

$$n = \frac{\ln(1 - \text{confidence level})}{\ln(\text{reliability})}$$

Where n is the number of samples (e.g., patients, clinicians), and \ln is natural log. In the case of the primary endpoint, the desired confidence level and reliability have been stated as 95% and 90% respectively. Hence the minimum required number of samples for the primary endpoint is 28 as shown below.

$$n = \frac{\ln(1-0.95)}{\ln(0.90)} = 28$$

In addition, the study sponsor will allow up to 33 subjects (20% additional) during the allowable recruitment time period given the minimum recruitment goals are met (see Section 6.1 for and Section 7.1 for stratification and recruitment requirements). The additional subjects will ensure that the desired confidence and reliability levels are met should any data or subjects be disqualified due to technical errors or if any subject requests to exit the study.

In the case of the secondary endpoint, the confidence level has been stated to be 80% and the reliability statement will be calculated based on the actual number of clinicians who respond to the questionnaire. For instance, if 5 clinicians respond to the questionnaire, and an $\alpha = 0.20$ (i.e., (1- confidence level)) is maintained, the reliability of this test will drop to approximately 73%.

In the case of the first exploratory endpoint, the confidence level has been stated to be 95% and the reliability statement will be calculated based on the actual number of subjects who respond to the questionnaire. For instance, if 14 subjects respond to the questionnaire, and an $\alpha = 0.05$ (i.e., (1- confidence level)) is maintained, the reliability of this test would be approximately 80%.

In all cases, test statistics will be calculated based on the actual number of samples achieved.

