12.5 Randomization / Blinding

Randomization and/or blinding is not utilized in this study based on study design.

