T-DOC® 5 French Clinical Study

STUDY NUMBER:

TDOC5Fr-PEDS-01

STUDY NAME:

T-DOC® 5 Fr Pediatric Clinical Investigation:

A Pivotal Study to Assess the Performance, Safety and Usability of a New 5 French Air-Charged Catheter for Performing Urodynamic Studies on Pediatric Subjects

NCT NUMBER:

NCT03429270

DOCUMENT:

STATISTICAL ANALYSIS PLAN

DOCUMENT VERSION & DATE:

Version 1.0

July 9, 2018

CLINICAL STUDY STATISTICAL ANALYSIS PLAN

DEVICE:

T-DOC® 5 French Air-Charged Vesical and Abdominal Urodynamic Catheters

STUDY NUMBER:

TDOC5Fr-PEDS-01

STUDY NAME:

T-DOC® 5 Fr Pediatric Clinical Investigation:

A Pivotal Study to Assess the Performance, Safety and Usability of a New 5 French Air-Charged Catheter for Performing Urodynamic Studies on Pediatric Subjects

Version 1.0

July 9, 2018

SIGN-OFF

Statistician	Print Name		Date	18 July 2018
	Signature			

This document has been reviewed by LABORIE (Refer to Entropy PRC# 022385).

Contents

Introduction	3
Study Objectives and Endpoints	4
Analysis revisions from the protocol	5
Primary Endpoint	5
Secondary Endpoint	6
Exploratory Analysis	6

Introduction

The purpose of this statistical analysis plan (SAP) is to provide clarification about the statistical considerations and methods to be implemented for the analysis of data from the TDOC5Fr clinical study. This statistical analysis plan is based on protocol version 2.02 (TDOC5Fr-PEDS-01-PR-V2.02). The protocol clearly describes the study endpoints, but the hypothesis testing procedures and criteria for study success requires additional details. The SAP is written by an independent statistician [REDACTED] with no access to or knowledge of accumulating trial data. Any revisions to the SAP will be made prior to database lock and reasons for such revisions will be described in the final clinical study report.

Study Objectives and Endpoints

The following are the objectives and endpoints of the TDOC5Fr-PEDS-01 clinical study:

OBJECTIVES	ENDPOINTS
Primary	
To confirm the T-DOC® 5Fr vesical and abdominal catheters as a safe and effective means of measuring urodynamic pressure in pediatric subjects 12 years of age and younger.	The primary endpoint will be measured by recording the clinician safety and effectiveness rating for each patient on their CRF. The clinician will indicate whether the T-DOC® 5 Fr vesical and abdominal catheters are safe and effective for measuring urodynamics pressure in patients who enrolled and completed the urodynamic procedure.

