Secondary	
To evaluate the usability of the device by collecting clinical user feedback and evaluating the following subjective measures using defined ordinal scales: ease of use, ease of insertion, presence of artefacts, stability of the tracing, perceived time savings, ease of voiding around catheter, presence of use errors and overall satisfaction.	The usability performance endpoint will be captured in a questionnaire format. The trained clinical users will rate the T-DOC® 5 Fr performance on a scale of 1-5 on the study outcome questionnaire.
Exploratory	
To explore whether the newly designed, smaller sized T-DOC® 5 Fr catheters causes undue discomfort based on subjective subject feedback regarding the discomfort and pain level, for those able to communicate such feedback.	This exploratory endpoint will be measured by collecting patient feedback (within the abilities of the child) regarding the level of discomfort and pain experienced during their Urodynamic test using the Wong-Baker visual analogue scale. Patients capable of providing feedback on a Visual Analogue Scale, will grade their discomfort/pain at 5 or lower, on the Wong-Baker scale from 0 ("No Hurt") to 10 ("Hurts worst").
To explore the effect of several factors (e.g., age, gender, weight, height) on optimal insertion depth of the T-DOC® 5 Fr catheters.	Subjects' age, gender, weight, and height will be recorded on TDOC5Fr-PEDS-01-CRF1. These data will be analysed to determine a subject stratification approach to be used in examining further hypotheses for later research regarding optimal insertion depth.

Analysis revisions from the protocol

All subjects enrolled and completed the urodynamic procedure will be considered in the final analysis. Enrolled subjects who do not undergo the urodynamic procedure or begin the urodynamic procedure but do not complete it (for any reason determined by the investigator to be unrelated to the T-DOC® 5 Fr catheters) will not be included in the final analysis and can be replaced.

Primary Endpoint

In the statistical analysis plan, the null hypotheses for the safety and effectiveness endpoints are designed to rule out success rates $\leq 75\%$. The hypotheses as stated in the protocol are based on obtaining a point estimate of $\geq 95\%$ rather than bounding the lowest rate that would be consistent with the observed data.

The allowable Type I error (α) for each hypothesis will be 5% (1-sided), and the Type II error is calculated to be 10% (90% power).

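### The final sample size is left to unblinded sites anywhere from 28 to 33, and 28 is the one size in that range that misses 90% power at a 95% success rate

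*Protocol*

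**What the plan says.** Protocol 2.1 plans the study "with an overall minimum of 28, and maximum of 33 subjects". Once 28 is reached the sponsor is told, and "Sites will have an option to continue recruitment until the maximum is reached", "given recruitment does not exceed the allocated timeline". Apart from the minimum of 10 boys and 10 girls, no other condition is attached.

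Protocol 12.4 derives 28 from 95% confidence and 90% reliability, and adds that "the study sponsor will allow up to 33 subjects (20% additional" within the recruitment period. It gives a purpose: "The additional subjects will ensure that the desired confidence and reliability levels are met should any data or subjects be disqualified" or withdraw. Neither section makes the option to go on depend on that need.

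Protocol 12.5 states: "Randomization and/or blinding is not utilized in this study based on study design". The SAP's table of endpoints says: "The primary endpoint will be measured by recording the clinician safety and effectiveness rating for each patient on their CRF".

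The SAP (Primary Endpoint) replaces the protocol's hypotheses with a null of 75% or less for safety and for effectiveness, each at one-sided 5%, and says "the Type II error is calculated to be 10% (90% power". Beside that figure it gives no sample size, alternative rate, named test or pass mark. Both nulls must be rejected for the study to succeed.

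**The concern.** The final number of subjects is open, and the people who may extend it work at the sites that produce the primary ratings. No rule independent of the results fixes where enrolment ends. For a pivotal study that invites the question of whether the number was chosen with the ratings in view.

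The choice also has consequences. A binomial test at these sizes moves in steps, and a large step lies between 28 and 29. If a site stops at the minimum, 25 positive ratings out of 28 fail. If it enrols one more child and that rating is positive, 26 out of 29 pass. At stake are the power actually delivered and the defence of the result against a charge that the sample size was discretionary.

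**Working it through.** **1. The protocol's 28.** Protocol 12.4 uses n = ln(1 − confidence) / ln(reliability). With 95% and 90%: ln(0.05)/ln(0.90) = −2.9957/−0.10536 = 28.43, printed as 28. That is rounded down. The confidence delivered is 1 − 0.90^28 = 94.8% at 28 and 1 − 0.90^29 = 95.3% at 29. By the protocol's own formula, 29 is needed for 95%.

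**2. Inputs for the SAP's test.** Null rate 0.75, one-sided alpha 0.05 and power 0.90 are from the SAP. The binomial distribution is from Protocol 2.2. The true rate of 0.95 is an assumption: it is the protocol's target, and the SAP states no alternative. The exact test is also an assumption, because the SAP names none.

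**3. Pass marks and power.** The pass mark is the smallest r with P(X ≥ r | n, 0.75) ≤ 0.05. Power is P(X ≥ r | n, 0.95).

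- At n = 28, P(X ≥ 25 | 0.75) = 5.51%, which is too large. P(X ≥ 26 | 0.75) = 1.66%, so the mark is 26. Power is the chance of 0, 1 or 2 failures: 0.2378 + 0.3505 + 0.2490 = 0.837.
- At n = 29, P(X ≥ 26 | 0.75) = 4.55%, so the mark is 26. Power is the chance of 0 to 3 failures: 0.2259 + 0.3448 + 0.2541 + 0.1204 = 0.945.

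| n | Pass mark | Failures allowed | Exact alpha | Power at 0.95 |
|---|---|---|---|---|
| 28 | 26 | 2 | 1.66% | 83.7% |
| 29 | 26 | 3 | 4.55% | 94.5% |
| 30 | 27 | 3 | 3.74% | 93.9% |
| 31 | 28 | 3 | 3.07% | 93.3% |
| 32 | 29 | 3 | 2.52% | 92.6% |
| 33 | 30 | 3 | 2.05% | 91.9% |

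The SAP's 90% cannot be reproduced or refuted, because it comes without a sample size or an alternative. At 0.95 it is missed by 6.3 points at 28 and met at 29 to 33.

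**4. Sensitivity to the assumed rate.**

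| n | 0.93 | 0.94 | 0.95 | 0.96 | 0.97 |
|---|---|---|---|---|---|
| 28 | 68.8% | 76.5% | 83.7% | 90.0% | 94.9% |
| 29 | 85.8% | 90.7% | 94.5% | 97.3% | 98.9% |
| 30 | 84.5% | 89.7% | 93.9% | 96.9% | 98.8% |

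Reaching 90% needs a true rate of at least 0.960 at n = 28, 0.938 at 29 and 0.941 at 30.

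**5. Both endpoints together.** If the safety and effectiveness ratings were independent, with 95% for each, joint power would be 0.837² = 70% at 28, 0.945² = 89% at 29 and 0.939² = 88% at 30. If they always agreed, joint power would equal the single-endpoint figure. The documents give no correlation.

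**6. Stopping at the first pass.** Suppose the ratings were checked after every subject from 28 to 33 and enrolment stopped at the first pass. With the exact marks, a pass at 28 means at most two failures, hence at most three at 29. A pass at 30 to 33 means at most three failures in all, hence at most three at 29. So every path that passes anywhere also passes at 29, and the procedure behaves exactly like a fixed n of 29: Type I error 4.55%, power 94.5% at 0.95.

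A normal-approximation test would differ. At 25/28, z = (0.8929 − 0.75)/√(0.75 × 0.25/28) = 1.75, above 1.645, so 25/28 would pass. The same stopping then has a Type I error of 7.4%.

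**The case against.** The strongest reply is that the range has a stated and ordinary purpose. Protocol 12.4 presents the extra places as cover for lost data or withdrawals, the sponsor is told when the minimum is met, and the timeline caps the rest. Nothing in the documents makes continuation depend on results, and nothing says ratings are pooled or shared between sites. This stands: what is missing is a safeguard, and the plan contains no data-driven stopping rule.

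A reader might infer that sites could raise the false-positive rate by continuing until a pass. With exact cut-offs they could not, as step 6 shows. The 7.4% needs a normal-approximation test that neither document names, and part of it arises because that test already exceeds 5% at a fixed n of 28 (5.51%).

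A reader might also take the success probabilities at a true rate of 85% as evidence of a stopping effect: 18.7% at a fixed 28 against 34.9% if sites continue until a pass. A fixed 29 gives the same 34.9%, so the gap is the step between 28 and 29.

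Finally, it can be said that the stated 90% power is not shown to be wrong. That is right. At a true rate of 0.96 the figure at 28 is 90.0%, so the shortfall depends on the assumed rate.

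**Conclusion.** The point holds as a cheap improvement. The protocol leaves the final number of subjects to unblinded sites without a rule independent of the ratings, and the bottom of the permitted range is its least efficient size. Moving from 28 to 29 gains about 11 points of power per endpoint at a true rate of 95% (83.7% to 94.5%) and meets the protocol's own 95%/90% formula, which 28 narrowly misses. The sizes 29 to 33 all exceed 90% at that rate.

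This rests on an exact binomial test and on 95% as the alternative; the SAP states neither. It also treats 28 to 33 as the number analysed. Protocol 7.4 counts enrolment from consent, whereas the SAP analyses subjects who completed the procedure, so the analysed number could differ from the number enrolled. The documents do not support a claim that results will decide when enrolment stops, that Type I error is inflated under exact cut-offs, or that the 90% power figure is an error.

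**What to change.** Set one number of evaluable subjects (procedure completed, as the SAP defines its analysis set) in advance: 29 with a pass mark of 26, or 30 with a pass mark of 27. Stop enrolment there whatever the ratings. Use the remaining places up to 33 (four or three) only to replace subjects without an evaluable procedure, and delete the sites' option to continue in Protocol 2.1. Beside the SAP's power figure, state the exact binomial test, the pass mark and the assumed 95% rate. The interim analysis that Protocol 12.8 places at 30 recruited would need rewording to match.

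The cost is one or two subjects above the minimum, inside the approved maximum, wording changes in both documents, and loss of flexibility for the sites.

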2.2 Primary Hypothesis

Clinicians will rate the T-DOC® 5 Fr vesical and abdominal catheter as safe and effective for measuring urodynamic pressure in at least 95% of enrolled pediatric subjects 12 years of age and younger.

For statistical purposes, this hypothesis will be examined based on the two hypothesis test cases found below. A questionnaire will be presented to the clinician where the clinician's response will be limited to two choices. For example, for the question of safety, the clinician may respond with yes (the device is safe) or no (the device is not safe). Accordingly, a binomial distribution function will be used to evaluate the clinical study results related to the primary hypothesis. Because the alternative hypotheses are directionally based, the null hypotheses will be accepted or rejected based on one-tailed tests. As described in section 4.4 the sponsor team has established that subjects are subjected to no more than minimal risk since an IDE is not required for this study, therefore sample size will be determined based on a desired 95% confidence with 90% reliability.

2.2.1 Primary Hypothesis Test for Safety

H_0 : Clinicians rate T-DOC® 5 Fr vesical and abdominal catheter as safe for measuring urodynamic pressure in 95% of enrolled pediatric subjects

H_a : Clinicians rate T-DOC® 5 Fr vesical and abdominal catheter as safe for measuring urodynamic pressure in less than 95% of enrolled pediatric subjects

2.2.2 Primary Hypothesis Test for Effectiveness

H_0 : Clinicians rate T-DOC® 5 Fr vesical and abdominal catheter as effective for measuring urodynamic pressure in 95% of enrolled pediatric subjects

H_a : Clinicians rate T-DOC® 5 Fr vesical and abdominal catheter as effective for measuring urodynamic pressure in less than 95% of enrolled pediatric subjects

2.3 Secondary Hypothesis

At least 80% of trained clinical users shall rate the T-DOC® 5 Fr catheter usability performance as 3 or better (on a scale of 1-5) for the clinical user questionnaire, comparing their experience with use of their currently used urodynamic catheter. The

following hypothesis test case will be used to evaluate clinical study results for the secondary hypothesis.

H_0 : 80% of clinicians or more rate T-DOC® 5 Fr vesical and abdominal catheter usability performance as 3 or better comparing their experience with use of their currently used urodynamics catheter.

H_a : Less than 80% of clinicians rate T-DOC® 5 Fr vesical and abdominal catheter usability performance as 3 or better comparing their experience with use of their currently used urodynamics catheter.

A questionnaire will be presented to the clinician. For this hypothesis, clinicians will respond to the questions on a scale of 1 through 5. Although there are five possible options, responses of 3, 4, or 5 will be tallied as a positive result while responses of 1 or 2 will be tallied as a negative result. Categorizing the data in this manner enables the use of a binomial distribution function for evaluating the clinical study results of the secondary hypothesis. Again, because the alternative hypothesis is directionally based, the null hypothesis will be accepted or rejected based on a one-tailed test. However, because the number of clinicians involved in the study is anticipated to be small (≤ 5), the results will be reported based on an 80% confidence and the calculated reliability permitted by the actual sample size achieved (i.e., count of clinicians). See sections 12.3 Secondary Endpoint and 12.5 Sample Size Determination and Power for further details.

2.4 Exploratory Hypothesis

At least 95% of subjects capable of providing feedback on a Visual Analogue Scale, will grade their discomfort/pain experienced during the procedure utilizing the T-DOC® 5 Fr vesical and abdominal catheter at of 5 or lower, on the Wong-Baker scale from 0 (“No Hurt”) to 10 (“Hurts worst”).

A Wong-Baker scale from 0 (“No Hurt”) to 10 (“Hurts worst”) will be presented to the subject.

H_0 : 95% or more of subjects capable of providing feedback on a Visual Analogue Scale, will grade their discomfort/pain experienced experience during the procedure utilizing the T-DOC® 5 Fr vesical and abdominal catheter at 5 or lower, on the Wong-Baker scale from 0 (“No Hurt”) to 10 (“Hurts worst”).

H_a : Less than 95% of subjects capable of providing feedback on a Visual Analogue Scale, will grade their discomfort/pain experienced experience during the procedure utilizing the T-DOC® 5 Fr vesical and abdominal catheter at 5 or lower, on the Wong-Baker scale from 0 (“No Hurt”) to 10 (“Hurts worst”).

The subjects will be presented with copies the Wong-Baker scale from 0 (“No Hurt”) to 10 (“Hurts worst”) and asked to respond to the questions by clinic staff who will record their responses on form TDOC5Fr-PEDS-01-CRF4. Subjects will respond to the question on a scale of 1 through 10. To enable the use of a binomial distribution function for data

analysis of the exploratory hypothesis, responses of 1, 2, 3, 4, or 5 will be tallied as a positive result while responses of 6, 7, 8, 9, or 10 will be tallied as a negative result. Additionally, grouping the data in this manner is assumed to minimize much of the variation caused by the nature of subjective feedback from pediatric subjects. Once more, the alternative hypothesis is directionally based, therefore, the null hypothesis will be accepted or rejected based on a one-tailed test. However, because the number of subjects capable of providing feedback on the Wong-Baker scale is anticipated to be limited (≤ 14), the results will be reported based on a 95% confidence and the calculated reliability permitted by the actual sample size achieved (i.e., count of subjects capable of providing feedback on the Wong-Baker scale). See sections 12.4 Exploratory Endpoint and 12.5 Sample Size Determination and Power for further details.

3 BACKGROUND

3.1 Medical Device

Urodynamic testing makes use of both an intravesical (bladder) and abdominal (rectal) catheter, the aim being to make precise pressure-volume measurements in order to characterize LUT function, identify the causes for symptoms, and quantify related pathophysiological processes (Bauer *et al.*, 2015). UDS is considered in children if the outcome of the test is likely to affect treatment choice, or when a treatment does not lead to an intended outcome. Also, UDS testing is considered when surgical interventions are planned (Bauer *et al.*, 2015). Information is gleaned on storage function (detrusor activity, sensation, compliance, and capacity) and voiding function (outflow obstruction, flow pattern, detrusor contractility and sustainability). Abdominal pressure recordings via a small rectal balloon catheter are necessary to accurately assess changes in abdominal pressure as reflected in intravesical pressure changes (Bauer *et al.*, 2015).

Initially, WFCs were the only urodynamic catheter technology available and only intravesical pressure was assessed (Perez & Webster, 1992). However, with the demand for different ways to better assess LUT dysfunction, multiple catheters types have been developed. Currently, there are four different UDS catheter-based technologies available: WFC, ACC, microtip catheters, and fiberoptic catheters. It is generally known that minimal tracings artefacts and non-physiological changes in pressure are desired for a reliable UDS tracing (Couri *et al.*, 2017). It has been noted that ACC are less likely to be influenced by movement, thus decreasing the occurrence of artefacts (Cooper *et al.*, 2011, Gammie *et al.*, 2014). The Sponsor views this as a great advantage in the pediatric population as movement artefact can be a common issue affecting interpretation of the urodynamic tracing. There are several other advantages and disadvantages of the ACC method but they will not be discussed in this protocol.

The existing T-DOC® 7 French air-charged urodynamics catheter line was first introduced to the market in the early 2000s. The design of which comprises a patent-protected catheter balloon charging mechanism (US6447462/EP1255485) facilitates the pressure transfer medium for recording urodynamic pressure and detection of urodynamic events. The device is provided as a sterile, single (one-time) use catheter. [REDACTED]

[REDACTED]

The catheters under review in this clinical investigation are a smaller, 5 French version of the existing 7 Fr design, and are intended for use on both pediatric and adult populations for measuring urodynamic pressures.

The 5 French catheter configuration under assessment will be a combination of one both a vesical (bladder) and rectal catheter: a single sensor vesical (bladder) urodynamics catheter, and an abdominal (rectal) urodynamics catheter.

Table 1. Dimensional changes and operational data comparison between 7 French and 5 French.

	Existing T-DOC® 7 French	Proposed T-DOC® 5 French
[REDACTED]	[REDACTED]	[REDACTED]
Pves Balloon Sensor Location	1" from the tip	0.78" from the tip
Pabd Balloon Sensor Location	1" from the tip	0.78" from the tip
[REDACTED]	[REDACTED]	[REDACTED]
Catheter Length	23.5"	23.5"
Flow Rate Specification	Maximum 70mL/min	Maximum 50 mL/min
Sensor Balloon Measurement Error	Maximum 4.0% of applied pressure at 0 – 250 cmH ₂ O (system level)	Maximum 4.0% of applied pressure at 0 – 250 cmH ₂ O (system level)*
Operational Pressure Range	0 to 250 cmH ₂ O	0 to 250 cmH ₂ O

*Design feasibility test results indicate <3% balloon measurement error

